*Principal investigator

** Sponsor

SECTION 1

1. Introductory Statement

Title: Autologous Cardiac Stem Cell Injection in Patients with Hypoplastic Left Heart Syndrome: An Open Label Pilot Study. (CHILD Study)

Sponsor: [name].
Interdisciplinary Stem Cell Institute
University of Miami Miller School of Medicine,
Division of Cardiology, Miami, Florida

Cell Manufacturing Center:
Interdisciplinary Stem Cell Institute
Clinical Research Cell Manufacturing (CRCMP) Program
University of Miami Miller School of Medicine
[name]
[name]

Test Agent: Autologous c-kit-positive cells (c-kit⁺ cells)

Population: Male or female neonates diagnosed with hypoplastic left heart syndrome (HLHS) undergoing Stage I Norwood operation.

Sample Size: A total of 32 subjects will be enrolled for this pilot study in a staged enrollment.

Treatment: All subjects with the diagnosis of hypoplastic left heart syndrome (HLHS) undergo a palliative reconstructive surgery performed in the first two weeks of life, termed the Norwood procedure. The Norwood procedure involves reconstruction of the aortic arch, resection of the atrial septum, and establishment of pulmonary blood flow through either a modified Blalock-Taussig shunt (mBTS) (a Gore-Tex tube from the innominate artery to the right pulmonary artery) or a Sano shunt (a Gore-Tex tube from the right ventricle to the right pulmonary artery). To initiate cardiopulmonary bypass for this surgery, the right atrial appendage is cannulated. Typically, the appendage is excised and discarded during this step. However, in our study, this excised right atrial appendage will be harvested and c-kit⁺ cells will be isolated. The process and manufacturing of the c-kit⁺ cells will be exactly as specified in the TAC-HFT II Study (IND# 14647, NCT00768066). TAC-HFT II was a Phase I/II, Randomized, Placebo-Controlled Study of the Safety and Efficacy of Transendocardial Injection of Autologous Human Cells (Mesenchymal or the combination of MSC and ckit+ in Patients with Chronic Ischemic Left Ventricular Dysfunction and Heart Failure Secondary to Myocardial Infarction trial of University of Miami under IND #14647. The patients will then proceed with the typical postoperative care. The second stage in the palliation of HLHS is a scheduled bidirectional cavopulmonary anastomosis, BDCPA) operation that

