Primary: Consistent with the nature of this study, multiple assessments will be performed to evaluate the safety, feasibility, and efficacy of intramyocardial delivery of c-kit⁺ cells in subjects with HLHS:

1. Safety will be assessed by monitoring the following major adverse cardiac events during the first 30 days post Stage II BDCPA operation:

- Greater than 30 seconds of sustained/symptomatic ventricular tachycardia requiring intervention with inotropic support or anti-arrhythmics
- Cardiogenic shock (i.e. tissue hypoperfusion presented by hypotension due to decreased cardiac output, determined by rising lactate levels (5x normal levels in first 24 hours, 2.5x normal levels in first 30 days)
- Unplanned cardiovascular operation due to right ventricular intramyocardial injection site bleeding in the first 5 days after Stage II BDCPA operation
- Need for new permanent pacemaker
- Stroke or embolic event to the brain determined by CT scan
- Death

2. Feasibility will be assessed by monitoring how many c-kit+ products can be manufactured and delivered to subjects and how many subjects can get baseline, 6-month and 12-month MRIs.
3. Efficacy will be assessed at 12 months post-Stage II BDPCA operation by change from baseline in right ventricular ejection fraction, right ventricular end-diastolic volume, right ventricular end-systolic volume, and tricuspid regurgitation measured by serial echocardiograms and MRI scans (baseline, 6 months and 12 months).

Secondary:

1. Incidence of mortality or need for transplantation after the Stage II BDCPA operation up to 12-month follow-up.
2. Incidence of the following after the Stage II BDCPA operation up to 12-month follow-up:
 - i. All-cause mortality
 - ii. Cardiovascular mortality
 - iii. Need for transplantation
 - iv. Hospitalization for heart failure
 - v. Cardiovascular morbidity, including myocardial infarction, stroke, heart failure, or sustained/symptomatic arrhythmias
3. Changes in somatic growth velocity (weight, length, head circumference) over 12 month follow-up.
4. Change in quality of life measured by the Infant Toddler Quality of Life Survey (ITQOL) at baseline, 6 and 12 months after Stage II BDCPA operation.

2. General Investigational Plan

A. Background

Surgical and Clinical Outcomes for HLHS

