We plan to enroll thirty-two patients with HLHS in a two staged enrollment process. In this study, a maximum of 21 patients will receive intramyocardial injection of c-kit⁺ cells and 11 standard of care control patients with no injection. The enrollment of the patients will occur in two staged groups: Group A and Group B. Initially in Group A, 10 consecutive HLHS patients will be enrolled in the c-kit⁺ cell treatment arm to determine feasibility and safety. Six months after the last patient is enrolled in Group A, the DSMB will conduct a review of all Group A patients in order to determine whether the methodology is feasible and safe, including the harvesting, processing, and administering of the c-kit⁺ cells. Thereafter, Group B will enroll a total of 22 HLHS patients which will be randomized, double-blinded to the treatment and standard of care control arms in a 1:1 ratio, respectively, in order to have 11 c-kit⁺ cell-treated patients and 11 control patients. Randomization will occur post-Norwood operation upon receipt of viable tissue sample at University of Miami Clinical Research Cell Manufacturing Program (CRCMP). The rationale underlying this two-staged enrollment is to initially test the feasibility and safety of this methodology of obtaining the c-kit⁺ cells from the right atrial appendage with the Group A patients. The second Group B patients may provide the required numbers to potentially validate the efficacy of the trial. Eventually, a Phase II trial will provide the necessary numbers to provide an accurate assessment of efficacy of the c-kit⁺ cells in HLHS patients.

B.1.2. Sample Size

Twenty-one (21) subjects will be enrolled in the treatment group and eleven (11) in the standard of care control group. The 10 Group A subjects are part of an open-label safety and feasibility analysis. The 22 Group B subjects will be randomized 1:1 to cell treatment and control to detect a difference of 6 RVEF units, given a standard deviation of 4, 89% power and type 1 error of 0.05. Twenty patients are needed with 10% added for possible lost to follow-up.

B.1.3. Dosage and Administration

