Prior to the Stage I Norwood operation, the subject's guardians will be given a complete explanation of the purpose of the study and evaluations to be performed which are in addition to those of standard of care. The Institutional Review Board (IRB) approved informed consent document will be reviewed with the guardians and any questions answered at that time.

The consent document (and the discussion with the guardians) will clearly outline the following:

- 1) the subject's guardians do not have to consent to this research for their child to receive the planned surgeries,
- 2) if the guardians want the subject to participate, there is a need for tissue sample collection to take place at the time of the Stage I Norwood operation (to enable study product to be manufactured) and consent is needed for this, if the subject is randomized to the standard of care group (i.e. no cells to be delivered) then the tissue will be discarded at the manufacturing facility.
- 3) there is a potential that the subject could be deemed ineligible for study participation prior to the Stage II BDCPA operation; for example, due to changes in health status, and
- 4) what a change in participation status would mean for any acquired tissue if the subject is discontinued from the protocol prior to the Stage II BDCPA operation.

Should the guardians consent to the study, a copy of the signed consent form will be provided to them at that time.

Prior to the Stage II BDCPA operation, the subject's guardians will be contacted to schedule appointments for research-related testing needed for determining continued eligibility. Before any testing is initiated, the consent form will be re-reviewed with the guardians to affirm their continued willingness to allow their child to participate. This re-review will be documented in the subject's chart. If the guardians are no longer interested in participation, the subject will be withdrawn from the study, and this will be noted in the subject's chart.

B.3.2. Screening Phase Assessments

The Screening Phase starts at enrollment and completes at the initiation of the harvest during the Stage I Norwood operation. The screening phase may last between 2 – 3 weeks, and will not alter the patient's pre-surgical duration.

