The following evaluations will be performed 21 days or less before Stage I Norwood operation (including right atrial tissue collection). These evaluations will include the following, which are routinely obtained for Stage I Norwood HLHS patients:

- a. Demographic data, including date of birth, gestational age, length, weight, gender, and race.
- b. Physical exam with vitals (length, weight, head circumference, oxygen saturation, heart rate, respiratory rate and blood pressure).
- c. Laboratory Assessments:
 1. Clinical chemistry: BUN, creatinine, sodium, potassium, chloride, glucose, calcium, bilirubin (total), total protein, albumin alanine aminotransferase (ALT), aspartate aminotransferase (AST), B-type Natriuretic Peptide (BNP).
 2. Hematology: complete blood count (CBC) with differential and platelet count
 - d. Assessment of mother's infectious disease status for HIV 1/2, hepatitis BsAg or viremic hepatitis C and syphilis (*Treponema pallidum*).
 - e. 12-lead electrocardiogram (ECG)
 - f. Concomitant medication history

The investigator may use clinical judgment when determining the clinical significance of laboratory parameter findings throughout the study.

During the screening phase, and prior to the tissue collection phase, the condition of the subject will be verified and key safety parameters will be assessed by the PI and study team to confirm feasibility of operation, including:

- Physical Examination
- Standard of Care pre-procedural labs
- ECHO results to determine valve status
- Tricuspid insufficiency
- Restrictive septum
- Poor RV function.

B.3.3. Tissue Collection Phase

B.3.3.a. Tissue Collection Procedures

The cell processing and manufacturing will be performed exactly as specified in the TAC-HFT II (A Phase I/II, Randomized, Placebo-Controlled Study of the Safety and Efficacy of Transendocardial Injection of Autologous Human Cells (Mesenchymal or the combination of MSC and Cardiac Stem Cells) in Patients

With Chronic Ischemic Left Ventricular Dysfunction and Heart Failure Secondary to Myocardial Infarction) trial of University of Miami (IND #14647). As specified, the tissues will be sent and processed at the University of Miami Clinical Research Cell Manufacturing Program (CRCMP), Interdisciplinary Stem Cell Institute.

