- Shipping Procedures - Tissue will be enclosed in a rigid shipping container with temperature insulating properties. Cold temperature packs will be used to maintain the shipping temperature between 2°C to

10°C. The rigid shipping container will include a document on the inside of the container and a label on the outside of the container according to Health Resources and Services Administration (HRSA) guidelines for organ transport policies and procedures. Shipping container will be accompanied by appropriate documentation including the “Chain of Custody form” with subject and sample unique identifiers, and a temperature logger. The vials containing the tissue will be shipped overnight using FEDEX to CRCMP (see cell processing manual for more detail).

B.3.3.b. Post Norwood Monitoring Phase (Standard of Care)

Following the completion of the Stage I Norwood operation and up to the Stage II BDCPA operation, all patients will be followed by both parent(s) and faculty per institutional standard of care. There will be no research-related procedures or data collected during this phase until the baseline visit and eligibility assessment.

B.3.3.c. Baseline Assessment

Prior to admission for the Stage II BDCPA operation, all subjects will undergo baseline testing and study eligibility determination as described below:

- a. Complete medical history including any co-morbidities such as central nervous system, renal, gastrointestinal and genetic abnormalities,
- b. Physical exam and vital signs (length, weight, head circumference, oxygen saturation heart rate, respiratory rate, blood pressure, and Modified Ross Score for heart failure classification (see Appendix A))
- c. 12 lead Electrocardiogram (ECG)
- d. Complete Trans-thoracic echocardiogram (TTE)
- e. Cardiac Magnetic Resonance Imaging (cMRI)
- f. A complete right and left cardiac catheterization, which is routinely performed before the Stage II BDCPA operation, if clinically indicated.
- g. Laboratory Assessments:
 1. Clinical chemistry: BUN, creatinine, sodium, potassium, chloride, glucose, calcium, bilirubin (total), total protein, albumin alanine aminotransferase (ALT), aspartate aminotransferase (AST), B-type Natriuretic Peptide (BNP).
 2. Hematology: complete blood count (CBC) with differential and platelet count
- h. Infant and Toddler Quality of Life (ITQOL) survey

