- i. Collection of Blood for Biomarker analysis of circulating pro-inflammatory markers (see MOP for blood collection and shipping instructions to CRCMP)

The research-only assessments listed above are the cMRI, ITQOL survey, and biomarker blood sample tests thus AE monitoring will begin when the first of these is performed.

B.3.3.d. Study Product Injection

The Stage II BDCPA operation occurs between 4 to 6 months of age. For Group B subjects randomized to study treatment, during this surgery when the patient is on cardiopulmonary bypass, the previously harvested c-kit⁺ cells will be injected into the right ventricle directly intramyocardially using a 25-27gauge needle syringe at the completion of the repair but before separating from cardiopulmonary bypass. The entire dose of the cells, up to 12,500/kg patient weight in 600 microliters, will be divided and delivered in 6-10 intramyocardial injections. The intramyocardial injection of cells will take approximately 5-10 minutes, which is insignificant to the total bypass time. The remaining part of the operation will proceed as anticipated.

B.3.3.e. Investigational Final Product Preparation

The harvested c-kit⁺ cells will undergo quality control testing and review by CRCMP laboratory director and quality assurance manager prior to release for clinical use. When the Stage II BDCPA operation is scheduled for subjects randomized to receive study product, upon request from the clinical site, product is shipped cryopreserved from CRCMP to the local cell processing laboratory in a validated vapor phase cryoshipper maintained at temperatures < -120 °C with a temperature monitoring device. Upon arrival, product is inspected to ensure that product is in good condition and the temperature data will be verified before transferring to the secured vapor phase storage freezer at the site. In the event that the temperature deviates from the specified shipping temperature, the product will not be used. Local cell processing laboratory notify CRCMP. The incident will be investigated with corrective and preventive actions implemented following the CRCMP standard operating procedures. CRCMP will prepare a new shipment of the product.

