All subjects will be cared for according to institutional standard postoperative protocols, which included standard of care post-surgery assessments. Research-related study visits will occur at Day 5 (\pm 3 days), Week 4 (30 days \pm 7 days), Month 6 (180 days \pm 30 days) and Month 12 (365 days \pm 30 days) (see Table 1). Data from standard of care visits can be used for study visits if collected within visit window. If a patient remains hospitalized at the planned visit date, the assessment will be performed as an inpatient.

The following assessments will be collected post-Stage II BDCPA operation (Day 0) visits as part of standard of care:

- a. Physical exam and vital signs (length, weight, head circumference, oxygen saturation, heart rate, respiratory rate, blood pressure, and Modified Ross Score for heart failure classification (see Appendix A))
- b. 12 lead electrocardiogram
- c. Complete TTE (Day 5, Month 6, and Month 12)
- d. Laboratory assessments at 5 days, 6 months, and 12 months:
 1. Clinical chemistry: BUN, creatinine, sodium, potassium, chloride, glucose, calcium, bilirubin (total), total protein, albumin alanine aminotransferase (ALT), aspartate aminotransferase (AST), B-type Natriuretic Peptide (BNP).
 2. Hematology: complete blood count (CBC) with differential and platelet count
- e. 24-hour Telemetry (Day 5)
- f. AE monitoring

The following research-related assessments will be collected post-Stage II BDCPA operation (Day 0):

- a. cMRI scan (Month 6 and Month 12)
- b. ITQOL survey (Month 6 and Month 12)

- c. Biomarker blood collection (Day 5, Month 6, and Month 12) (See MOP for collection and shipping instructions)

Table 1

Test/Procedure	Pre-Norwood	Pre-BDCPA	BDCPA	Post-BDCPA			
		Baseline ¹	Day 0	Day 5 ± 3 days	Week 4 30 days ± 7 days	Month 6 180 days ± 30 days	Month 12 365 days ± 30 days
Informed Consent	X						
Demographics	X						
Medical History		X					
Physical Exam ²	X	X		X	X	X	X
Lab Assessments ³	X	X		X		X	X
Infectious disease testing ⁴	X						
ECG	X	X		X	X	X	X
ITQOL survey		X				X	X
Trans-thoracic Echo (TTE) ⁵		X		X		X	X
MRI ⁵		X				X	X
Cardiac Cath ⁶		X					
Randomization ⁷	X						
Study Product Injection (SPI)			X				
Telemetry				X			
Biomarker blood collection		X		X		X	X
Adverse Event Monitoring		X	X	X	X	X	X

1 – Baseline testing should preferably occur within 30 days of Stage II BDCPA operation (Day 0), however can occur up to 90 days before

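### The DSMB review that opens Group B is timed from Group A enrolment, so it can fall before the last Group A infant has completed the 30-day primary safety window

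*Combined protocol and SAP*

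**What the plan says.** Section B.1.1 (Basic Design Characteristics) states: "Six months after the last patient is enrolled in Group A, the DSMB will conduct a review of all Group A patients". The review is to decide whether the method is feasible and safe, and the section names harvesting, processing and administering the cells. Group B enrols after it.

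The other times come from elsewhere in the protocol:

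- **Enrolment.** B.3.2: "The Screening Phase starts at enrollment and completes at the initiation of the harvest during the Stage I Norwood operation". The clock therefore starts before the Norwood operation.
- **Norwood.** Section 1, Treatment: "performed in the first two weeks of life".
- **Between Norwood and baseline.** B.3.3.b: "There will be no research-related procedures or data collected during this phase until the baseline visit and eligibility assessment".
- **Injection.** B.3.3.d: "The Stage II BDCPA operation occurs between 4 to 6 months of age".
- **Primary safety endpoint.** Section 1, Endpoints: "major adverse cardiac events during the first 30 days post Stage II BDCPA operation".
- **Visit that closes the window.** B.3.3.f and Table 1 place the Week 4 visit at 30 days, plus or minus 7.

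No section makes the review wait for the last Group A infant to have had Stage II or to have completed the 30 days after it.

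**The concern.** The six months run from an event near birth, while the safety data begin at an operation 4 to 6 months later. Most of the interval is therefore not study follow-up, since B.3.3.b excludes research data collection until the baseline visit. If the last infant's Stage II comes late in its stated range, the DSMB is asked whether administering the cells is safe while that infant's primary safety window is still open.

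At stake is the data behind the decision to move from the open-label stage to the randomised stage. Group A has ten infants, so one incomplete record is a tenth of the planned safety experience. Others enrolled shortly before the last infant could be incomplete as well.

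**Working it through.** The plan gives no figure of its own for follow-up at the review, so there is none to reproduce. The check is calendar arithmetic on the protocol's times, with 1 month = 30.44 days.

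**Inputs**

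- Review: 6 months after the last Group A enrolment (B.1.1).
- Age at enrolment, E: 0 to 14 days, because enrolment precedes a Norwood operation done by about day 14 (B.3.2; Section 1, Treatment).
- Age at Stage II, s: 4 to 6 months (B.3.3.d).
- Primary safety window: 30 days after Stage II (Section 1, Endpoints). The Week 4 visit may fall as late as day 37 (Table 1).

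**Days of follow-up after injection at the review**

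F = E + (6 − s) × 30.44

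| Age at enrolment | s = 4 months | s = 5 months | s = 6 months |
|---|---|---|---|
| Birth (E = 0) | 60.9 | 30.4 | 0 |
| Day 14 (E = 14) | 74.9 | 44.4 | 14.0 |

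**Latest Stage II age with the 30 days complete**

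Setting F = 30 gives s = 6 − (30 − E)/30.44.

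- E = 0: 6 − 30/30.44 = 5.01 months.
- E = 14: 6 − 16/30.44 = 5.47 months.

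Allowing for the Week 4 visit at day 37, the limits are 6 − 37/30.44 = 4.78 months and 6 − 23/30.44 = 5.24 months. All four lie inside the stated range for Stage II.

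**Shortfall with Stage II at 6 months**

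- E = 0: 30 − 0 = 30 days (37 with the visit limit).
- E = 14: 30 − 14 = 16 days (23 with the visit limit).

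**How often.** The documents give no distribution of Stage II age. If it were spread evenly over 4 to 6 months (an assumption, for scale only), the window would be open at the review in 26% (E = 14) to 49% (E = 0) of cases.

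**Sensitivity to enrolment before birth.** B.3.2 allows a screening phase of 2 to 3 weeks. If enrolment were 21 days before birth (E = −21, an assumption), follow-up would be 39.9, 9.4 and −21.0 days for Stage II at 4, 5 and 6 months. The limit would be 6 − 51/30.44 = 4.32 months.

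**Group B exposure.** The earliest Group B injection is in an infant enrolled on the review date at 14 days of age with Stage II at 4 months: 121.8 − 14 = 107.8 days later. With Stage II at 6 months, the last Group A window closes, counting the visit limit, 37 days after the review if E = 0, or 58 days if E = −21. The margin is 107.8 − 37 = 70.8 days, or 107.8 − 58 = 49.8 days.

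**The case against.** The strongest objection is that little follows in practice. The margin just shown means that no Group B infant receives cells before the missing Group A data exist, provided Stage II stays within 4 to 6 months. The primary safety events would ordinarily count as serious under D.2.1, and C.3 and D.6 send serious events to the DSMB as they occur. D.6 also allows ad hoc meetings, and D.7 allows enrolment to be halted. This stands, and it limits the severity. It does not supply what the review lacks: reports of events so far do not show that an infant has completed 30 days without one.

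Second, B.1.1 speaks of enrolment into the treatment arm, and eligibility is rechecked before Stage II (B.3.3.c). If enrolment meant entry at that point, six months would easily cover the window. But B.3.2 places enrolment at the start of screening, before Norwood. If the sponsor meant a later event, B.1.1 still needs to name it.

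Third, D.6 leaves details to a DSMB charter that is not among the documents, and the charter may set a minimum follow-up. It cannot be assumed to do so, and B.1.1 would still state a different trigger.

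Fourth, the prenatal case is strained, because screening includes the infant's own weight, vital signs and ECG. That is fair; the conclusion does not depend on it.

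Finally, the shortfall is conditional and is calculated for one infant only. With Stage II at 4 months there is none.

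**Conclusion.** The concern holds. Followed as written, B.1.1 can hold the review with the last Group A infant's primary safety window still open. This happens if Stage II is later than about 5.0 months (enrolled at birth) to 5.5 months (enrolled at day 14). At the late end of the stated range, that infant has only 0 to 14 days of follow-up after injection. The result rests on the protocol's own times and on reading enrolment as B.3.2 uses it. The review would come before the injection itself only if enrolment is before birth or Stage II is after 6 months.

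This should be fixed because the stated rule can give a less informed decision at the protocol's formal checkpoint. It is not a problem of immediate exposure for Group B.

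**What to change.** Replace the calendar trigger in B.1.1 with an event trigger. Hold the review once the last Group A subject to receive cells has completed 30 days after Stage II and the Week 4 visit, and every other Group A subject has been injected or has left the study before injection. The trigger should refer to the last subject injected, who need not be the last enrolled. At the review, report how many Group A subjects were injected and how many have complete 30-day data. State in the DSMB charter how the review proceeds if the last Stage II operation is postponed, since the trigger is otherwise open-ended.

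The cost is one sentence in B.1.1, submitted as an amendment for IRB review, and a matching line in the charter. No patients or procedures are added. If Stage II is early enough for the window and visit to be complete by six months, there is no delay. With Stage II at 6 months, Group B opens later by 16 to 23 days (enrolled at day 14) or 30 to 37 days (enrolled at birth). The delay would be 51 to 58 days under the assumed enrolment 21 days before birth, and longer in any of these cases if Stage II is postponed beyond 6 months.

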The treated HLHS patients will receive up to 12,500 cells/kg. The terminology “up to” a certain dose indicates that if the number of the c-kit⁺ cells is not sufficiently attainable from the cardiac specimen to the specified dose then the achievable dose will be delivered. A secondary analysis of subjects who achieve ≥80% of the assigned dose will be performed as part of the overall analysis plan. The decision to weight-adjust the dose of cells was made based on preclinical studies. The cells will be delivered through 6-10 intramyocardial injections of approximately 100uL per injection for total volume of 0.6 mL

B.1.4. Premature Withdrawal

For subjects withdrawn after receiving study product injection, all efforts will be made to encourage return for all assessments through the end of the study period, so that safety can continue to be monitored.

Because the data from the proposed trial may be used to design future phases of clinical trials, we put a high priority on collecting data that is complete and accurately describes the safety and efficacy of the intervention as described. Therefore, the goal is to have final MRI and other efficacy endpoint measurements on at least 20 Group B subjects during the randomized portion of trial. As such, Group B study treatment subjects who do not undergo the stem cell injection or do not get the Stage II BDCPA operation can diminish the goal sample size of 20. A maximum of six additional subjects can be randomized to replace this potential loss to achieve the target sample size of 20 evaluable subjects.

B.2. Criteria for Subject Enrollment

B.2.1. Inclusion Criteria

For inclusion in the study, subjects must meet all of the inclusion criteria:

1. Subjects with hypoplastic left heart syndrome (all types) requiring Stage I Norwood operation.

B.2.2. Exclusion Criteria

Candidates will be excluded from the study if any of the following conditions are met:

1. Subjects undergoing the Stage I Norwood operation who do not have HLHS.
2. Subjects requiring mechanical circulatory support immediately prior to Stage II BDCPA operation (within 5 days).

3. Parent or guardian unwilling or unable to comply with necessary follow-up(s).
4. Mother is serum positive for HIV 1/2, hepatitis BsAg or viremic hepatitis C and *Treponema pallidum*.
5. Subjects who are unsuitable for inclusion in the study in the opinion of the investigator(s).

B.3 Sequence of Measurements and Evaluation

B.3.1. Subject Introduction and Informed Consent

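### The 30-day MACE denominator in C.2 includes infants who never reach Stage II, and the B.1.4 replacement trigger does not match its own goal of measured subjects or the C.2 analysis by assigned arm

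*Combined protocol and SAP*

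**What the plan says.** **Timing.** B.1.1: "Randomization will occur post-Norwood operation upon receipt of viable tissue sample". B.3.3.d places Stage II at 4 to 6 months of age. B.3.1 warns guardians that "there is a potential that the subject could be deemed ineligible for study participation prior to the Stage II BDCPA operation", and B.2.2 excludes infants who need mechanical circulatory support in the five days before Stage II. Loss between randomisation and Stage II is therefore foreseen, in either arm.

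**Safety.** Section 1 (Endpoints, Primary, item 1) counts the listed major adverse cardiac events (MACE) in the 30 days after Stage II. C.2 defines the Safety Analysis Set (SAS) as all of Group A plus all of randomised Group B, with no condition on having had Stage II, and assigns the primary safety analysis to it.

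**Replacement.** In B.1.4, "the goal is to have final MRI and other efficacy endpoint measurements on at least 20 Group B subjects". It continues: "Group B study treatment subjects who do not undergo the stem cell injection or do not get the Stage II BDCPA operation can diminish" that number. Then: "A maximum of six additional subjects can be randomized to replace this potential loss to achieve the target sample size of 20 evaluable subjects". Evaluable is not defined, and control infants are not mentioned.

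**Efficacy analysis.** C.2 puts every randomised subject in the Efficacy Analysis Set (EAS), by assigned arm. C.5 bases the main analysis on available data.

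**Sample size.** B.1.2: "Twenty patients are needed with 10% added for possible lost to follow-up". C.6 spreads this as one subject per group and gives 89% power for 10 against 10, with a difference of 6 RVEF units and SD 4.

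**The concern.** A safety proportion should be taken over subjects who could have had the event. An infant who dies, is withdrawn or becomes ineligible before Stage II belongs to the SAS but never enters the MACE window. Such infants enlarge the denominator without any possibility of adding to the numerator, so the error runs towards looking safer, in a study whose first objective is safety and feasibility.

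The replacement rule decides how many infants are randomised. Its stated goal is measurement, but its triggers are receipt of injection and receipt of Stage II, and only in the treatment arm. Two infants are then handled oddly:

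- A treatment-arm infant who has Stage II, is not injected and completes both MRIs supplies exactly the data the goal asks for, yet can count against the 20.
- A control infant who misses Stage II supplies no final measurement after Stage II, yet is not named.

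C.5 says the bioactivity results will inform endpoints and sample size for larger trials. The plan should therefore say who makes up the 20, and whether the 6-unit difference is between assigned arms or an effect in injected infants.

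**Working it through.** **1. The plan's own power figure.** Inputs from C.6: difference 6, SD 4, two-sided alpha 0.05, 10 per arm. Two-sample t-test with noncentrality 6 / (4 × √(1/10 + 1/10)) = 3.354 on 18 degrees of freedom: power 88.7%. The stated 89% is reproduced.

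**2. MACE on the SAS.** Let N be the number in the SAS, k the number who never reach Stage II, and p the true 30-day rate among those who do. The expected proportion on the SAS is p × (N − k)/N, so the relative understatement is k/N, whatever p is. The plan gives no value for k or p. Two scenarios, both with no Group A losses:

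- k = 2: 22 − 2 = 20 remain, so no replacement is needed. N = 10 + 22 = 32, and 2/32 = 6%.
- k = 4: 22 − 4 = 18 remain, so two replacements. N = 34, and 4/34 = 12%. This assumes all four losses lead to replacement, which B.1.4 provides for only in the treatment arm. Without replacement, 4/32 = 12.5%.

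**3. How each infant is treated under B.1.4 and C.2.**

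| Group B infant | Has final MRI (B.1.4 goal) | Named in B.1.4 as a loss | In EAS (C.2) | In main analysis (C.5, available data) |
|---|---|---|---|---|
| Treatment, Stage II, injected, both MRIs | Yes | No | Yes | Yes |
| Treatment, Stage II, not injected, both MRIs | Yes | Yes | Yes | Yes |
| Treatment, no Stage II, no final MRI | No | Yes | Yes | No |
| Control, no Stage II, no final MRI | No | No | Yes | No |

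In the second and fourth rows the trigger and the goal disagree.

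**4. What non-injection would do to ITT power.** The plan gives no rate, so the following is conditional. Assume 6 units is the effect in injected infants, uninjected infants have no effect, the SD is 4 within each subgroup, and all 11 + 11 are measured. Simulated pooled t-test, 400,000 trials per case:

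| Uninjected of 11 | Expected ITT difference | Power |
|---|---|---|
| 0 | 6 | 92% |
| 1 | 6 × 10/11 = 5.5 | 84% |
| 2 | 6 × 9/11 = 4.9 | 73% |

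If the SD is instead held at 4 for the whole treatment arm, 1 or 2 uninjected gives 86% or 78%.

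**5. What non-injection as a trigger buys.** With 2 uninjected, 20 remain, no replacement is due, and power is 73% either way. With 4 uninjected, B.1.4 as written allows two more subjects (one per arm, giving 8 injected + 4 uninjected against 12): 55%. Without them (7 + 4 against 11): 46%.

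**The case against.** **A reader might infer that B.1.4 and C.2 contradict each other.** They do not. B.1.4 governs how many infants are randomised, and C.2 governs who is analysed. Recruiting extra subjects while analysing everyone by assigned arm is coherent. B.1.4 also says only that these infants can diminish the target and speaks of a potential loss. That an uninjected infant counts against the 20 even with a final MRI is an inference from non-injection being listed separately without exception.

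**A reader might infer that controls are ignored.** The text does not go that far. The 10% attrition covers one loss per group, the target is 20 Group B subjects overall, and additional subjects are randomised, so they go to both arms. What stands is that the trigger for replacement names one arm only.

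**A reader might infer that the power claim is wrong or the attrition allowance too small.** The 89% is correct. C.6 defines the difference simply as one between two means; read as a difference between assigned arms, it already includes any non-injection. B.1.3 provides for giving whatever dose is achievable, so low cell yield need not mean no injection. The 60% one-year survival in the Background is no basis for judging the 10%: it comes from a 1994 to 2000 series of neonates with critical aortic stenosis or atresia, and does not give the loss after randomisation in this trial.

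**On safety,** the plan states no MACE proportion or test. C.3 describes event profiles and listings, C.1 leaves detail to an SAP finalised before database lock, and an all-subject set suits feasibility. This makes the understatement conditional on a proportion being reported. It does not remove the problem, because C.2 as written assigns the primary safety analysis to that set.

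**Conclusion.** Two clarifications are needed, of minor to moderate weight.

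The firmer one is the MACE denominator. As written, infants who were never at risk are included, and any proportion is biased downwards by k/N. The 6% and 12% figures rest on assumed losses; the direction does not.

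The second is that the replacement trigger fits neither the stated goal of measured subjects nor the analysis by assigned arm, evaluable is undefined, and control losses are unnamed.

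The power statement needs no correction. Whether non-injection would erode it depends on what the 6 units represent and on a non-injection rate that the documents do not give. Bioactivity is declared exploratory, which limits the consequences.

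**What to change.** - **C.2.** For the 30-day MACE, use as denominator the subjects who underwent Stage II, grouped by treatment received. Report subjects who did not reach Stage II separately, by assigned arm. Keep the full SAS for feasibility.
- **B.1.4.** Define evaluable as having baseline and 12-month MRI, counted in the assigned arm. Make the replacement trigger the same in both arms: Stage II not performed. If non-injection is kept as a trigger, call it a top-up and state that all randomised subjects stay in the EAS.
- **C.6 (optional).** Say whether 6 units is the difference between assigned arms or the effect in injected infants. If the latter, note that 89% assumes no non-injection, and give the power for one or two uninjected.

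**Cost.** Wording only: no new data, and no subjects beyond the six already allowed. There are two real downsides. The MACE comparison would condition on reaching Stage II, a post-randomisation event, which is why those not reaching it should be shown by assigned arm. And if uninjected infants no longer trigger replacement, ITT power is lower when several are uninjected (46% against 55% with four, under the assumptions above), which is the reason for leaving the top-up open.
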